A total sample size of 300 subjects (150 subjects per arm) yields approximately 99% power to establish superiority of TP-03 to vehicle in the subjects meeting the primary efficacy endpoint assuming a response rate of 80.0% in TP-03 and 15.8% for vehicle treatments, respectively using a Pearson chi-squared test with a one-sided significance level of 0.025. Response rates for sample size calculations are based upon a prior outside United States clinical study of TP-03, 0.25%, and vehicle for the treatment of *Demodex* blepharitis.

Similarly, 300 subjects (150 subjects per arm) yields 99% and 99% power to establish superiority of TP-03 to vehicle treatment in the proportion of subjects with *Demodex* eradicated and the proportion of subjects with a composite of collarette and erythema cure respectively at Day 43 assuming a response rate of 73.3% in TP-03 and 21.1% in vehicle and 73.3% in TP-03 and 10.5% in vehicle using a Pearson chi-squared test with a one-sided significance level of 0.025.

The study will be considered a success and TP-03, 0.25%, will be considered superior to vehicle in clinical cure if H_{01} is rejected in favor of H_{11} . With this sample size, the study will have > 95% power to claim success for clinical cure. If in addition to success for clinical cure, H_{02} is rejected in favor of H_{12} , the study will also claim superiority of TP-03, 0.25%, to vehicle in *Demodex* eradication. Similarly, if in addition to success for clinical cure, H_{03} is rejected in favor of H_{13} , the study will also claim superiority of TP-03, 0.25%, to vehicle in composite collarette and erythema cure. With this sample size, the study will have > 95% power to claim success for clinical cure and superiority for both *Demodex* eradication and collarette and erythema cure.

Accounting for a 30% discontinuation, approximately 209 subjects per arm (approximately 418 total) will be randomized. The planned enrollment is much greater than typically planned to achieve 300 completed subjects due to concerns regarding the impact of COVID-19, and the possibility that up to two sites may be unable to complete the study.

6. Data Preparation

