8.2 Missing or Inconclusive Data Handling

The primary efficacy analysis will be conducted with missing data and intercurrent events handled in the following manner:

- Discontinuation of study medication and non-optimal compliance is ignored [treatment policy strategy].
- Withdrawal due to lack of efficacy or AEs: missing data will be imputed as failure [hypothetical strategy].
- Missing data without withdrawal or withdrawal due to reasons other than lack of efficacy or AEs: missing data will be imputed employing Multiple Imputation (MI) using randomized treatment-based Markov Chain Monte Carlo (MCMC) methodology [hypothetical strategy].

In the event that the percentage of missing data due to discontinuation of study medication and non-optimal compliance exceeds 2%, these missing data will be imputed as failures and the primary efficacy analysis repeated in a separate analysis.

Sensitivity analyses on the primary efficacy endpoint are described in the Efficacy Analysis section.

Partial/missing start and end dates for AEs and concomitant medications will be imputed as follows:

Partial/missing start date:

- Dates with missing day only will be imputed as the 1st of the month unless the month and year are same as the month and year of first dose of study medication, in which case missing day will be imputed as the first dose day of study medication.
- Dates with both day and month missing will be imputed as 1 Jan unless the year is same as the year of first dose of study medication, in which case missing day and month will be imputed as the first dose day and month of study medication.
- Completely missing dates will be imputed as the first dose date of study medication unless the end date is on or before the first dose date of study medication, in which case missing date will be imputed as 1 Jan of the same year as the end date.

Partial/missing end date:

- Dates with missing day only will be imputed as the last day of the month unless the month and year are the same as the month and year of the last dose of study medication, in which case missing day will be imputed as the last dose day of study medication.

- Dates with both day and month missing will be imputed as 31 Dec unless the year is same as the year of the last dose of study medication, in which case missing day and month will be imputed as the last dose day and month of study medication.

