An overall summary will be presented that includes the number of events and the number and percentage of subjects who experienced at least one TEAE, by treatment group and over all subjects. This summary will also include breakdowns of TEAEs further categorized as ocular or non-ocular, treatment-related TEAEs, serious adverse events (SAE), TEAEs leading to death, and TEAEs by maximum severity.

Ocular and non-ocular TEAEs will be summarized using discrete summary statistics and presented by treatment group at the subject and event level by SOC and PT. If a subject reports the same PT multiple times, that PT will only be counted once within that SOC. As with the PT, if a subject reports multiple conditions within the same SOC, that SOC will only be counted once. In the summary, SOCs will be summarized in ascending alphabetical order; PTs will be listed in order of descending frequency for all subjects within each SOC.

Separate summaries will be provided for the following categories of AEs:

- Ocular TEAEs
- Non-ocular TEAEs
- Ocular TEAEs by SOC, PT, and Severity
- Non-ocular TEAEs by SOC, PT, and Severity
- Ocular TEAEs by SOC, PT, and Strongest Relationship to Study Drug
- Non-ocular TEAEs by SOC, PT, and Strongest Relationship to Study Drug
- Ocular TEAEs by SOC, PT, Severity, and Strongest Relationship to Study Drug
- Non-ocular TEAEs by SOC, PT, Severity, and Strongest Relationship to Study Drug
- TEAEs That Led to Premature Discontinuation
- Treatment-emergent SAEs

Summaries of TEAEs by maximum severity will be presented for ocular AEs and non-ocular AEs separately. The number of subjects with any TEAEs (along with percentages) will be tabulated by SOC and PT within each SOC by treatment group. To count the number of subjects with any TEAEs, if a subject has multiple TEAEs coded to the same PT, the subject will be counted once under the maximum severity.

All AEs and TEAEs will be presented in a subject listing. The TEAEs leading to study treatment discontinuation and resulting in temporary discontinuation of study drug will be listed separately. In addition, all SAEs will be presented in a separate listing.

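### Failure imputation is tied to withdrawal and its recorded reason, so a subject who stops study drug for an AE or lack of efficacy and misses Day 43 can still be imputed as a possible cure

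*SAP*

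**What the plan says.** SAP Section 8.2 gives three rules for the primary analysis.

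- Stopping study medication, or taking it imperfectly, is ignored under a treatment policy strategy.
- "Withdrawal due to lack of efficacy or AEs: missing data will be imputed as failure".
- "Missing data without withdrawal or withdrawal due to reasons other than lack of efficacy or AEs: missing data will be imputed employing Multiple Imputation", fitted within randomized arm.

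A further paragraph adds a repeat analysis if "the percentage of missing data due to discontinuation of study medication and non-optimal compliance exceeds 2%, these missing data will be imputed as failures". It is separate from the primary analysis, and the text does not say what the 2% is a percentage of.

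The imputation code in Section 13.1 runs by treatment on the baseline, Day 8, Day 15, Day 22 and Day 43 grades. Nothing in it represents stopping drug. Section 13.2 carries the same approach to both secondary endpoints.

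Two other places matter. The study-exit reasons to be summarized in Section 9 are AE, significant non-compliance, pregnancy, exclusion criteria, COVID-19 and other; lack of efficacy is not among them. Section 14.2 shows that AE-related drug stops can be identified: "The TEAEs leading to study treatment discontinuation and resulting in temporary discontinuation of study drug will be listed separately".

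**The concern.** Section 8.2 does not define withdrawal. Because stopping medication has its own rule, the natural reading is withdrawal from the study. Take two TP-03 subjects who stop drug for the same AE and have no Day 43 grade. If one exits with AE recorded, that subject is a failure. If the other stays nominally in the study and misses Day 43, or exits as non-compliant or other, that subject is multiply imputed and may be counted as cured.

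The clinical course is the same, and the primary outcome depends on how the exit is coded. The credit is larger on TP-03, where most imputed values come from an arm expected to do well, so the bias favours TP-03. The lack-of-efficacy half of the failure rule has a further problem: with no such category in Section 9, it may not be derivable, and those exits could fall under other and go to imputation. What is at stake is the size of the reported effect and a clearly defined estimand.

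**Working it through.** **Inputs from SAP Section 5.** "A total sample size of 300 subjects (150 subjects per arm) yields approximately 99% power", "assuming a response rate of 80.0% in TP-03 and 15.8% for vehicle treatments", "using a Pearson chi-squared test with a one-sided significance level of 0.025". Also "Accounting for a 30% discontinuation, approximately 209 subjects per arm (approximately 418 total) will be randomized".

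**Inputs assumed.** The documents do not give the share f of subjects who stop drug for an AE or lack of efficacy and miss Day 43 without a withdrawal so recorded. I take f from 1% to 30%.

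**1. The plan's own figures.** With 150 per arm the pooled rate is (0.80 + 0.158)/2 = 0.479.
- Null SE = sqrt(2 × 0.479 × 0.521/150) = 0.0577.
- Alternative SE = sqrt((0.80 × 0.20 + 0.158 × 0.842)/150) = 0.0442.
- z = (0.642 − 1.96 × 0.0577)/0.0442 ≈ 12.0, so power exceeds 0.9999, consistent with the stated 99%.
- 150/0.70 gives 215 per arm, against the stated 209, which corresponds to 1 − 150/209 = 28.2% loss. The gap is small and does not affect this point.

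**2. Shift if these subjects are imputed at the arm rate.** Shift in TP-03 cure relative to failure = f × 0.80. The corresponding vehicle shift is f × 0.158. The planned difference is 80.0 − 15.8 = 64.2 points.

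| f | TP-03 cure if failures | Difference, TP-03 only affected | Difference, both arms affected |
|---|---|---|---|
| 1% | 79.2% | 63.4 | 63.6 |
| 2% | 78.4% | 62.6 | 62.9 |
| 5% | 76.0% | 60.2 | 61.0 |
| 10% | 72.0% | 56.2 | 57.8 |
| 30% | 56.0% | 40.2 | 44.9 |

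Power stays above 0.9999 in every row. For scale, the SE of the difference with 209 per arm is sqrt((0.16 + 0.133)/209) = 3.7 points.

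**3. What the specified imputation would assign.** The model conditions on the subject's own earlier grades, so the arm rate is only a reference value. I checked this with an illustrative normal model for TP-03, using the SAP's variables, its 0 to 4 bounds and its rounding. Assumptions: 80% at grade 0 on Day 43, baseline spread over grades 2 to 4, latent correlation 0.2 to 0.8, and out-of-range draws either redrawn or clipped.

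| Observed grades (baseline, Days 8, 15, 22) | Imputed cure probability | Points per 1% of TP-03 | Points for 8 of 209 |
|---|---|---|---|
| 3, 3, 3, 3 (non-responder) | 0.09–0.45 | 0.09–0.45 | 0.3–1.7 |
| 3, then nothing | 0.39–0.60 | 0.39–0.60 | 1.5–2.3 |
| 3, 1, 0, 0 (early responder) | 0.47–0.90 | 0.47–0.90 | 1.8–3.4 |
| Reference: arm rate | 0.80 | 0.80 | 3.1 |

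The last column is 8 × probability/209. Values below 0.80 reflect the subject's grades and the bounded, rounded normal draws. None reflects an allowance for being off drug. Every value exceeds the zero given to the subject whose exit is recorded as AE.

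**4. The 2% trigger.** If the denominator is randomized subjects pooled over arms, 8/418 = 1.91% does not trigger it and 9/418 = 2.15% does. If the denominator is missing values, 30% of 418 is about 125, and 8/125 = 6.4% triggers it. The text does not settle which applies.

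**The case against.** A reader might infer that these subjects are imputed at about the TP-03 on-drug cure rate. The documents do not support that as a general statement. The model uses each subject's earlier grades, and someone stopping for lack of efficacy will usually have high ones. Observed off-drug Day 43 grades also stay in the model under treatment policy, so the arm's data are not purely on-drug. About 80% is near the top of the plausible range; only a subject already responding approaches or passes it.

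A reader might also infer that nothing else picks these subjects up when the 2% trigger is not met. That is not so. Sensitivity V always sets all missing data to failure, Sensitivity I always imputes from vehicle, and Sections 13.2.1 and 13.2.2 add an all-failure analysis for each secondary endpoint. The trigger is nowhere said to be pooled over arms. It also counts non-compliance and drug stops for any reason, so it is easier to reach than eight cases on one arm suggests. Lack-of-efficacy stops could fall mainly on vehicle.

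Finally, the public protocol contains only its summary. Its rules for leaving the study cannot be seen, and the class may be small.

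All of this stands and limits the size. It does not remove the point. Sensitivity V also fails every COVID-19 and administrative loss, in a trial planned around 30% discontinuation, so it cannot isolate this class. Sensitivity I does not isolate it either. Neither changes the primary estimate, where the same course can still be scored in opposite ways.

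**Conclusion.** The point holds as a gap in the primary missing-data rule with a modest upward bias in TP-03 cure. The bias is about 0.8 points per 1% of TP-03 subjects affected at the arm rate, and illustratively 0.1 to 0.45 for persistent non-responders. With 2% affected in both arms, the arm-rate shift in the difference is 2 × 0.80 − 2 × 0.158 = 1.3 points. A subject with an AE recorded as the exit reason is already a failure and is not part of the problem.

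This rests on reading withdrawal as study withdrawal, on an assumed frequency, and on assumed score distributions and correlations. It would be wrong to infer that the trial's conclusion is at risk: at the planning rates significance is secure throughout the range examined. The effect is on the size of the estimate and on whether site coding can decide a subject's outcome. It is worth correcting because the plan already intends that AE and lack-of-efficacy losses should not count as cures.

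**What to change.** Make these changes before unmasking.

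- Define withdrawal in Section 8.2, and reword the failure rule. A missing Day 43 score after permanent discontinuation of study drug for an AE or lack of efficacy is a failure, whatever the study-exit status or recorded reason.
- Restrict multiple imputation to the remaining missing data.
- Apply the same rule to both secondary endpoints.
- Identify AE-related stops from the AE data. For lack of efficacy, use a reason where one is recorded, and add that category to the recorded reasons. The visible text does not show that it is collected now.
- Run the separate analysis that treats drug-discontinuation missingness as failure without the 2% trigger, and report the counts by arm.

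The cost is SAP wording, one derivation and possibly one added reason category. The TP-03 cure rate may come out slightly less favourable.

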- If the ongoing flag is missing or “Yes” then the date will not be imputed unless death date is available, in which case the missing date will be imputed as the death date. If ongoing is “No” then the missing end date will be imputed as the last dose date.
- If the imputed date is after the date of death, then the end date will be set equal to the date of death.

The original dates will be displayed in data listings and the imputed dates will be used in derivations only (study day, treatment-emergence status, etc).

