11.2 Concomitant Medications

Concomitant medications will be coded using World Health Organization Drug Dictionary (WHO DRUG) Global (B3, March 2020) and summarized to the therapeutic drug class (Anatomical Therapeutic Chemical [ATC] 4 classification) and preferred name. If the ATC 4 classification is not provided, the next lowest classification that is provided in the coding dictionary will be used. The preferred name will be defined as the active ingredient; if the active ingredient is not provided or includes more than two ingredients (e.g., multivitamins) then the drug name will be summarized as the preferred name.

Concomitant medications are defined as those medications listed as having been taken (1) prior to initiation of study drug administration and continuing for any period of time following the first administration of study drug or (2) at any time following the first administration of study drug.

Concomitant medications will be summarized using the safety set. Medications will be tabulated for each treatment group using frequencies and percentages. Subjects may have more than one medication per ATC text. At each level of subject summarization, a subject will be counted once if he/she reports one or more medications. Percentages will be based on the number of subjects in each treatment group.

Summaries will be sorted in decreasing frequency. Listings of concomitant medications will be generated separately for ocular and non-ocular data, including indication, route of administration, start date, and end date or ongoing.

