14.2 Adverse Events

An Adverse Event (AE) is defined as any untoward medical occurrence associated with the use of a drug in humans, whether or not the event is considered drug-related. All AEs will be coded using the MedDRA version 23.0.

Treatment-emergent adverse events (TEAE) are defined as any event that occurs or worsens on or after the day that randomized study treatment is initiated. It is not anticipated that any AEs will occur before treatment. However if in the unlikely event an AE recorded in the eCRF which began prior to treatment will not be included in the summary tables but will be included in the AE data listings.

Severity of an AE is defined as a qualitative assessment of the degree of intensity of an AE as determined by the Investigator or reported to him/her by the subject. The assessment of severity is made irrespective of relationship to study drug or seriousness of the event and should be evaluated according to the following scale:

- **Mild** - Events require minimal or no treatment and do not interfere with the subject's daily activities.
- **Moderate** - Events result in a low level of inconvenience or concern with the therapeutic measures. Moderate events may cause some interference with functioning.
- **Severe** - Events interrupt a subject's usual daily activity and may require systemic drug therapy or other treatment. Severe events are usually potentially life-threatening or incapacitating.

The relationship of each AE to the study drug should be determined by the Investigator using these explanations:

- **Definitely Related** – Evidence indicates a reasonable temporal sequence of the event with the study drug administration exists or that the association of the event with study drug administration is unknown and the event is not reasonably supported by other conditions such that:
 - There is a clinically plausible time sequence between onset of the AE and study treatment administration; and/or
 - There is a biologically plausible mechanism for study treatment causing or contributing to the AE; and
 - The AE cannot be reasonably attributed to concurrent/underlying illness, other drugs or procedures.

- **Potentially Related** – Evidence indicates a possible relationship to the study drug such that:

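### SAP 8.2: two of the three start-date imputation rules ignore a known end date, so an adverse event that ended before first dose can be counted as treatment-emergent

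*SAP*

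**What the plan says.** SAP section 8.2 gives three rules for start dates of AEs and concomitant medications.

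- **Day missing.** The 1st of the month is used unless month and year match first dose, "in which case missing day will be imputed as the first dose day of study medication".
- **Day and month missing.** 1 January is used unless the year matches first dose, "in which case missing day and month will be imputed as the first dose day and month of study medication".
- **Completely missing.** The first-dose date is used "unless the end date is on or before the first dose date of study medication". In that case the start becomes 1 January of the end-date year.

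The only other consistency check is about death: "If the imputed date is after the date of death, then the end date will be set equal to the date of death". On how the results are used, the section says "the imputed dates will be used in derivations only (study day, treatment-emergence status, etc".

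Section 14.2 defines a treatment-emergent AE (TEAE) by occurrence or worsening from the day treatment starts. It adds that an AE "which began prior to treatment will not be included in the summary tables". Section 11.2 treats a medication as concomitant if it was started earlier and continued past first dose, or was taken "at any time following the first administration of study drug".

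**The concern.** Moving an uncertain start to the first-dose date is a conservative convention: if an event might have begun on treatment, count it as treatment-emergent. That reasoning fails once the record shows the event was over before the first dose. The third rule recognises this and checks the end date. The first two do not, although they apply to records with more date information.

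Followed to the letter, they give a start after the end and then pass that start to the TEAE flag. At stake is whether the AE summaries count only what section 14.2 says they should, and whether programmers must choose between an impossible date order and an undocumented departure from the SAP.

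**Working it through.** No figure in the plan needs reproducing, so the check applies the section 8.2 rules literally.

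**Notation.** F is the first-dose date, E a complete recorded end date and S the imputed start.

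**Rules (section 8.2).**
- Day missing, month and year equal to those of F: S = F.
- Day and month missing, year equal to that of F: S = F.
- Completely missing, E on or before F: S = 1 January of the year of E.

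**Flag (sections 8.2 and 14.2).** The AE is a TEAE if S is on or after F.

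Under either of the first two rules, S − E = F − E, which is positive for every E before F. The start is always after the end, and the flag is always set. Under the third rule S cannot be later than E.

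**Illustration.** The documents give no individual dates, so assume F = 15 March 2021.

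| Start as recorded | Known end E | Imputed start S | S − E (days) | TEAE by rule |
|---|---|---|---|---|
| Day missing, March 2021 | 5 March | 15 March | 15 − 5 = +10 | Yes (wrong) |
| Day and month missing, 2021 | 20 January | 15 March | 11 + 28 + 15 = +54 | Yes (wrong) |
| Completely missing | 5 March | 1 January | −63 | No (right) |
| Day missing, February 2021 | 20 February | 1 February | −19 | No (right) |
| Day missing, March 2021 | 20 March | 15 March | −5 | Yes (as intended) |

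Rows 1 and 3 have the same end date. The record with no start information is classified correctly; the one with a known month is not.

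**All possible earlier end dates.**
- Same month, day missing: 1 to 14 March, 14 of 14 give S after E.
- Same year, day and month missing: 31 + 28 + 14 = 73, and 73 of 73 give S after E.

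The counts depend on the assumed F. In general they are the day of the month of F minus 1 (0 to 30), and the day of the year of F minus 1 (0 to 364 in a 365-day year). That every such date fails does not depend on F. These are counts of possible dates, not expected records.

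**Medications.** Take row 1 as a medication. Judged by its recorded end of 5 March, it neither continued past 15 March nor was taken afterwards, so it meets neither part of the section 11.2 definition. Judged by S = 15 March alone, it looks as if it was taken from first dose onward and would be flagged. The SAP does not say which date drives the flag.

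**Corrected rule.** If E is before F, use the 1st of the known month, or 1 January of the known year. Row 1 becomes 1 March and row 2 becomes 1 January; neither start is after its end and neither is a TEAE. Row 5 stays at 15 March and remains a TEAE.

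**The case against.** The strongest reply is that the affected set is close to empty. Table 2 of the SAP schedules AE review from Day 1, not at Screening, and section 14.2 does not expect AEs before treatment. A misclassified AE would have to be recorded even though it began and ended before first dose, have a partial start date matching first dose, and have a complete earlier end date. Original dates also stay in the listings, so an odd record can be traced. All of this stands, and it sets the severity.

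The second reply concerns medications, which are reviewed from Screening and are the likelier place for such records. A reader might infer that a medication stopped before first dose will be counted as concomitant. The documents do not compel that. Section 11.2 turns on actual use after first dose, a complete end date is never imputed, and section 8.2 does not name concomitant status among the derivations that use imputed dates. The miscount arises only if the flag is built from the imputed start alone.

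Neither reply removes the AE result. Section 8.2 names treatment-emergence status as a use of imputed dates, and no text stops an imputed start from passing a known end.

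**Conclusion.** The rule is wrong as written, with low severity. For AEs, a partial start matching first dose plus a known earlier end date gives a TEAE that section 14.2 would exclude. For medications the error is conditional on programming. The documents allow no estimate of the number of records; few are likely. The same rules apply in both arms, and the records concerned predate treatment, so the expected effect is slightly inflated counts with no systematic difference between arms. No efficacy endpoint, test or sample-size figure is involved.

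A reader might go on to infer a matching fault in the end-date rules. When the ongoing flag is No, "then the missing end date will be imputed as the last dose date", and for an event beginning in the Cohort 2 follow-up after treatment that end would precede its start. The documents do not support treating this as a fault with consequences. Onset after first dose already fixes treatment-emergent and concomitant status whatever end date is imputed, and the AE summaries listed in section 14.2 cover counts, severity and relationship, with no analysis of duration. It changes no planned summary.

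The conclusion assumes a literal reading of section 8.2 and no further date-order check in the programming specifications, which are not among the documents.

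**What to change.** In SAP section 8.2, extend the end-date condition of the third start-date rule to the first two. If the known end date is before the first-dose date, impute the 1st of the known month (day missing) or 1 January of the known year (day and month missing). Add one general sentence: an imputed start date may never be later than a known end date.

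The third rule uses on or before. For the first two, strictly before is enough: a record ending on the first-dose day gets start equal to end, which is coherent, and keeps the conservative treatment-emergent status.

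In section 11.2, a short statement that a known end date before first dose rules out concomitant status would settle the medication flag.

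The cost is a few clauses and a small programming change, with no new data. It should be settled before unmasking.

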4.1 Method of Assigning Subjects to Treatment Groups

A subject who meets all of the inclusion criteria and none of the exclusion criteria and has provided written informed consent is eligible for randomization at Day 1.

In this study, subjects will be instructed to administer a single drop of the study product twice a day (e.g., morning and evening) in each eye. The treatment period will be for approximately 43 days.

At Day 1, site staff will supervise the subject's first dose of the study medication. Subjects will be asked to wash their hands prior to administration. Following drop instillation, the subject will be advised to close their eyes for approximately 15 to 30 seconds and apply gentle pressure to the upper lid to express the medication across the upper and lower lid margins. The subject should be instructed to let the medication air dry on the lid without dabbing with a tissue.

During waking hours, if a dose is missed in the morning, subjects will be instructed to administer the drop if it is at least an hour prior to the second dose of the day. If it is less than an hour, the subject should simply dose the second drop of the day.

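### SAP 8.2 dates an adverse event of unknown start that ended on the first-dose day to 1 January, so it drops out of the TEAE tables although 14.2 counts that day as on treatment

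*SAP*

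**What the plan says.** SAP 8.2 introduces its date rules with "Partial/missing start and end dates for AEs and concomitant medications will be imputed as follows". For a start date with no recorded part the default is: "Completely missing dates will be imputed as the first dose date of study medication". That default holds "unless the end date is on or before the first dose date of study medication". If the end date does fall there, the start becomes 1 January of the year in which the event ended.

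The two partial-start rules in 8.2 work differently. If only the day is missing and the month and year match those of the first dose, or if only the year is known and matches, the start is set to the first-dose date. Neither rule looks at the end date.

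For an event that is not ongoing and has no end date, 8.2 says "then the missing end date will be imputed as the last dose date". On the use of these values it says "the imputed dates will be used in derivations only (study day, treatment-emergence status, etc".

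SAP 14.2 defines a TEAE as "any event that occurs or worsens on or after the day that randomized study treatment is initiated". An adverse event that began before treatment appears in the listings but not in the summary tables.

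**The concern.** The two sections put the boundary in different places. In 14.2 the first-dose day belongs to the treatment period. In the exception in 8.2, an end date on that same day is enough to push an unknown start back before treatment.

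The day matters for an instilled product. SAP 4.1 says "At Day 1, site staff will supervise" the first dose, and the visit schedule in SAP Table 2 starts adverse event review on Day 1. A brief same-day reaction would have exactly this end date.

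SAP 2.1 makes treatment-related adverse effects the primary safety endpoint, and 14.2 builds the treatment-related category from TEAEs. All the adverse event summaries named in 14.2 are TEAE or treatment-emergent SAE summaries. So an event that the investigator judged related to study drug could drop out of every one of them because of an imputed 1 January start.

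**Working it through.** The plan states no figure on this point, so there is none to reproduce. The check applies the rules to the boundary case.

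**Inputs.** F = first-dose date; E = recorded end date; S = imputed start when the start is completely missing (8.2). An event is a TEAE by date if S ≥ F (14.2). Planned randomization is 209 per arm, 418 in total (SAP section 5).

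**Rule as written.** If E ≤ F, then S = 1 January of the year of E; otherwise S = F.

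**Boundary case, E = F.** The condition E ≤ F is met, so S = 1 January of the year of F. S ≥ F then holds only if F is 1 January. Taking each day of an assumed 365-day year (2021) as F, the event is classed as not treatment-emergent for 364 of 365 first-dose dates.

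**Rule with strict inequality.** If E < F, then S = 1 January of the year of E; otherwise S = F. With E = F, S = F, and the event is a TEAE for 365 of 365 first-dose dates.

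**Example, assuming a first dose on 15 February 2021.** From 1 January to 15 February is 31 + 14 = 45 days.

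| Recorded end date | As written | Strict inequality |
|---|---|---|
| 14 February | start 1 January (study day -45), not a TEAE | same |
| 15 February | start 1 January (study day -45), not a TEAE | start 15 February (study day 1), TEAE |
| 16 February | start 15 February (study day 1), TEAE | same |

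In this example only the boundary day changes.

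**Comparison with the partial-date rules.** Take the event that ended on 15 February. If its start were recorded as February 2021, or as 2021 alone, 8.2 would set the start to 15 February and the event would be a TEAE. With nothing recorded about the start, the classification reverses.

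**Size per case.** A subject with no other TEAE who is lost in this way lowers the arm's TEAE incidence by 1/209 = 0.48 percentage points, and the all-subjects incidence by 1/418 = 0.24 points. The documents give no rate of missing start dates, so an expected number of cases cannot be derived.

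**Missing end dates.** Suppose start and end are both missing, the event is not ongoing, and the subject dosed on Day 1 only. The end date is imputed as the last dose date, which equals F. If the exception reads that imputed value, S is again 1 January. The SAP does not say whether end dates are imputed before the check.

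**The case against.** The strongest reply is that a pre-treatment start may be right. A reaction that began and ended on the day of a witnessed dose is the event least likely to have no start date at all, not even a year. Screening can precede Day 1 by up to 14 days, adverse event review is first scheduled on Day 1, and 14.2 provides for recorded events that began before treatment. An unknown start with a Day 1 end fits such an event too. This stands as far as true onset goes: it is unknown. It is only partly offset by the remark in 14.2 that no pre-treatment events are anticipated.

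A reader might therefore infer too much: that these records are probably first-dose reactions, and so certainly misclassified. The documents do not support that. What is certain is the class that the rule assigns, not that the class is wrong.

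Other points also stand. SAP 6.1 requires edit checks and query resolution before lock, which may recover the date. All adverse events are listed with their original dates, and SAEs have their own listing. Recorded worsening on or after Day 1 could still make an event a TEAE under 14.2. The rule is the same in both arms and touches no efficacy test. The route through an imputed end date depends on an order of imputation that the SAP does not state, so it is a request for clarification and not a demonstrated loss.

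None of this explains why the exception includes the first-dose day, or why it departs from the partial-date rules beside it.

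**Conclusion.** The concern holds as a narrow boundary conflict. An adverse event with a completely missing start and an end date on the first-dose day is always classed as pre-treatment, except when the first dose falls on 1 January. This conflicts with the day-based definition in 14.2 and with the partial-date rules in 8.2. Because onset is unknown, some of these events will be true TEAEs and some will not; the rule resolves all of them away from treatment-emergence, which is the anti-conservative direction for safety.

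The case is rare and the point is minor. The size is 0.48 points of arm-level incidence per affected subject, assuming 209 dosed subjects in the arm and no other TEAE in that subject. The finding rests on a literal reading of the exception and on the statement in 8.2 that imputed dates determine treatment-emergence status. It does not show that any event would in fact be lost, or that the arms would be affected unequally.

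**What to change.** In SAP 8.2, for adverse events only, limit the exception for completely missing start dates to end dates strictly before the first-dose date. An event that ended on the first-dose day then takes the first-dose date as its start and counts as a TEAE.

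Leave the concomitant-medication rule as it is. The present sentence covers both, and for a medication stopped on Day 1 an earlier start may well be reasonable.

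Add a clause that the check uses recorded, not imputed, end dates. If part of an end date is recorded and that part already places it in a month or year before the first dose, it should count as recorded evidence; otherwise the imputed start could fall after the end.

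The cost is a short SAP edit before unmasking and one changed condition in the adverse event derivation. Efficacy analyses, sample size and trial procedures are untouched. The downside is that an occasional event that began before the first dose and ended on Day 1 may be counted as a TEAE, which is conservative for safety.
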